**6.0 RECRUITMENT PLAN**

Patients will be evaluated by attending physicians from the Departments of Neurosurgery and Radiology entered onto the study if they are appropriate candidates. The attending physician will obtain informed consent from the eligible patient.

**7.0 ASSESSMENT/EVALUATION PLAN**

Patient assessment and evaluation will be based on region-of-interest (ROI) measurements of tumor, non-tumor-bearing brain, the dural venous sinus/arterial blood pool, as well as additional data from whole blood/plasma radioactivity measurements. These assessments will be used to obtain static and dynamic  $^{18}\text{F}$ -FLT uptake measurements, namely SUV values and estimated kinetic rate constants (including proliferation) using both voxel-wise and ROI-based tracer kinetic modeling approaches. SUV values and rate constants will be compared with molecular markers (percentage of Ki-67 and CD31 expressing cells, differential gene expression signatures) determined at corresponding sites of biopsy. This evaluation is detailed in Section 4.0.

**8.0 TOXICITIES/SIDE EFFECTS**

The radiotracer,  $^{18}\text{F}$ -FLT, has been synthesized by the MSKCC cyclotron facility for about two years, and has been used in humans in this and other institutions in this country and Europe. The primary source of the FLT will be the MSKCC cyclotron facility; however, alternative commercial sources are available to ensure consistent supply of FLT. If a commercial supplier of FLT is used for a particular study, the supplier will be required to meet all of the acceptance criteria outlined in the FDA-approved MSKCC FLT IND (#104742) prior to administration.  $^{18}\text{F}$ -FLT synthesized at MSKCC has been tested for toxicity and pyrogenicity. The product synthesized at MSKCC has met all requirements. No side effects are expected as a result of this study. However, in the unlikely event that an adverse reaction to the radiopharmaceutical occurs, the results must be documented and reported by the Principal Investigator to the Institutional Review Board Chairman and IND Committee.

**9.0 PRIMARY OUTCOMES**

Primary study measurements will be FLT uptake (SUV values); estimated rate constants, including that reflecting proliferation, derived from voxel-wise and ROI-based tracer kinetic modeling; and molecular markers (percentage of Ki-67 and CD31 expressing cells, differential gene expression signatures).

**IRB  
PB**

**Amended: 12/27/11**

Memorial Sloan-Kettering Cancer Center  
IRB Protocol

IRB#: 09-060 A(4)

## 10.1 CRITERIA FOR REMOVAL FROM STUDY

10.1.1. Patients will not be removed from the protocol unless they request so.

10.1.2. If at any time, the patient develops unacceptable protocol-associated toxicity, he/she will be removed from study.

10.1.3. If at any time the patient is found to be ineligible for the protocol, as designated in the section on Criteria for Patient/Subject Eligibility (i.e., a change in diagnosis), the patient will be removed from the study.

## 11.0 BIOSTATISTICS

This is a pilot study intended to collect preliminary data on 15 patients diagnosed with untreated high-grade glioma who are scheduled to undergo surgical resection.

Primary Aim: To investigate relationships between voxel-based determinations of proliferation rate and observed MR imaging features, as well as with spatially registered histologic measures of tumor cell proliferation (Ki67) and microvascular density (CD31) at corresponding locations.

Statistical Methodology for Primary Aim: In this aim, we will first explore the relationships between  $^{18}\text{F}$ -FLT PET parameters and MR imaging features ( $K_{\text{trans}}$  or microvascular permeability). The  $^{18}\text{F}$ -FLT PET parameters:  $K_1$  (tracer delivery rate constant),  $k_2$  (rate constant reflecting flow from the tumor interstitial compartment back to blood),  $k_3$  (rate constant reflecting proliferation), and  $k_4$  (rate constant reflecting flow from tumor cells back into the tumor interstitial space) will be compared to  $K_{\text{trans}}$  on MR imaging. We will also explore relationships between  $K_{\text{trans}}$ , each of the  $^{18}\text{F}$ -FLT PET parameters, and the histological markers Ki67 and CD31. All of the parameters and markers are measured on a continuous scale. Initially graphical methods such as pair-wise scatter plots will be used to assess the relationships. The relationships between each pair of variables will be more formally evaluated using methods that account for correlated data (there may be up to four observations per patient) such as random effects regression models or generalized estimating equations.

It is unlikely but possible that it may be determined at surgery that a patient does not have a high-grade glioma but instead has a metastasis or PCNSL. The likelihood that this will occur will be infrequent, if at all, given the constellation of distinctive imaging features that generally serve to differentiate these tumor types. If it does occur, however, we will continue accrual until 15 high grade glioma patients have been enrolled. In this case, two sets of analysis for the primary aim and all other aims will occur, one including all enrolled patients and one including only patients with high-grade gliomas. Patients found to have a metastasis or PCNSL may not yield different values than patients with glioma so the decision to include them in the analysis may not be unreasonable.

**Memorial Sloan-Kettering Cancer Center  
IRB Protocol**

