## 1.1 PROTOCOL SUMMARY AND/OR SCHEMA

This is a baseline feasibility study using fluorine-18-labeled fluorothymidine ( $^{18}\text{F}$ -FLT), a proliferation tracer, and highly focal MR image-guided biopsy to evaluate whether characteristic metabolic/MR imaging findings can be linked to distinct molecular phenotypes and improve our understanding of the molecular and pathological heterogeneity within individual tumors. In addition, this study will assess the feasibility of voxel-wise estimation of proliferation and tracer delivery from overall FLT uptake assessments, as against traditional ROI-based pharmacokinetic approaches. The quantitative accuracy of these parametric images will be investigated through comparison of histologic determinations of tumor cell proliferation, CD31 expression, and gene expression differences, obtained at different biopsy locations, with the PET-MRI imaging features at those same locations. The results of these studies will lay the groundwork for larger prospective studies assessing  $^{18}\text{F}$ -FLT proliferative response in trials of targeted therapy, relating estimates of proliferation with prognosis, survival, and clinical outcome.

Please note that all patients entered on this protocol will undergo the standard of care for their brain tumor. The information obtained from the use of  $^{18}\text{F}$ -FLT PET scans will NOT be used to guide patients' surgical planning on this protocol. Since FLT PET is considered investigational, subjects enrolled in this protocol will only undergo FLT PET scans under an FDA-approved institutional IND (#104742).

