### **3.5 Multimodal Image-Guided Surgical Targeting:**

With the exception of one recent investigation in which multiple targeted biopsy specimens were retrieved along a single biopsy tract, image-based measurements of  $^{18}\text{F}$ -FLT uptake have not been made in the region of histologic sampling. Given the high degree of heterogeneity of glial tumors, it would be preferable to correlate several imaging measurements per patient with histologic analyses in the same areas of the tumor in order to detail relationships between tumor metabolism, physiology, and specific malignant features. Local relationships between histologic features and radiotracer uptake or anatomic/functional MR imaging findings will additionally influence image analysis and interpretation of gliomas. Multimodal image-guided stereotactic biopsies have been previously performed by co-registering functional MR and PET imaging studies. By combining anatomic scans with metabolic and functional data from PET imaging, complementary information may be obtained that permits tumor heterogeneity and extension to be better defined, in addition to adding prognostic value. These studies have sought to detail relationships between functional imaging parameters reflecting tumor vascularity (relative microvascular blood volume, rCBV) and tumor metabolism using  $^{11}\text{C}$ -methionine or  $^{18}\text{F}$ -FDG, and their relationship to malignant features, MVD, or VEGF by histopathologic correlation. However, these correlations generally relied on representative tissue samples obtained from biopsy or resection, not in the region of image-based measurements. Thus, local comparisons between imaging and tissue measurements could not be performed. Correlations between brain tumor  $^{18}\text{F}$ -FLT uptake and histopathologic proliferation markers have also been based on representative biopsy or resection specimens. Neuronavigated surgery, however, facilitates increased precision of tissue sampling at locations that correspond with imaging measurements.

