All analyses are purely exploratory and intended to generate data for future studies. We do not plan to conduct any rigorous hypothesis testing. To explore what we might be able to say using this limited sample size, we find that with data on 15 patients we expect to be able to detect a moderately high correlation coefficient of 0.60 with 80% power using a two-sided 0.05 level test. This calculation assumes that each patient contributes only one observation, but in our case, we expect an average of two observations for each patient (up to four samples per patient) which may increase our power to draw any conclusions. Simulation studies assuming an average of two observations per patient indicate that we can estimate the concordance correlation coefficient to within (half-width of 95% confidence interval)  $\pm 0.27$  for a CCC equal to 0.8,  $\pm 0.20$  for a CCC equal to 0.9, and  $\pm 0.05$  for a CCC equal to 0.99.

**Memorial Sloan-Kettering Cancer Center  
IRB Protocol**

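### The planned single-slope clustered regressions cannot show whether FLT kinetics track Ki67 or CD31 within a tumour or only differ between patients

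*Combined protocol and SAP*

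**What the plan says.** Section 11.0 (Statistical Methodology for Primary Aim) starts with pairwise scatter plots. It then evaluates each pair of variables by "methods that account for correlated data", because "there may be up to four observations per patient", and gives examples: "such as random effects regression models or generalized estimating equations". The pairs link the four FLT rate constants, Ktrans, Ki67 and CD31. Secondary Aim #2 applies the same methods to Ki67 against SUV and Ki67 against k3.

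The aim is spatial. It concerns "spatially registered histologic measures of tumor cell proliferation (Ki67) and microvascular density (CD31) at corresponding locations". Section 1.1 wants to understand "molecular and pathological heterogeneity within individual tumors", and Section 3.5 argues that "it would be preferable to correlate several imaging measurements per patient with histologic analyses in the same areas of the tumor".

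Nowhere does the plan centre a variable within patient, add a patient mean as a covariate, or say whether a reported slope is within-tumour or between-patient. The only contrast framed within an individual is the gene-expression power statement for the exploratory aim.

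**The concern.** A random intercept or a GEE working correlation deals with the standard error. It does not change the fact that one coefficient on the raw imaging value has to serve two different relationships:

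- **Within a tumour:** do sites with higher k3 than the rest of the same tumour also have higher Ki67?
- **Between patients:** do patients with higher average k3 have higher average Ki67?

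These can differ. Section 5.1 admits both newly diagnosed and recurrent tumours, and the all-patients analysis in Section 11.0 would keep any metastasis or PCNSL. Either could shift imaging and histology together at patient level. The pooled slope could then be positive with no local relation, or a real local relation could be weakened by patients who differ for other reasons. The comparison of SUV with k3 in Secondary Aim #2 inherits the same ambiguity. Targeted biopsy, intraoperative MRI and post-hoc registration produce data that can answer the local question, but the planned summary does not isolate that answer.

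**Working it through.** **Inputs from Section 11.0.** n = 15 patients; up to four sites each, two expected on average, so about 15 × 2 = 30 observations; random-effects or GEE models.

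**Assumptions (not in the documents).** Patient share of variance (ICC, written ρ), between-patient correlation rb and within-tumour correlation rw. Total variances are set to 1.

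**The plan's own figure.** No figure in the plan bears directly on this point. The nearest is 80% power for a correlation of 0.60 (15 patients, two-sided 0.05), computed with one observation per patient. That is a correlation across patients and cannot separate the levels. It recomputes to 0.67 (Fisher z), 0.70 (exact bivariate normal) or 0.77 (fixed-regressor noncentral t). That is a separate matter, and nothing below depends on it.

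**Step 1: the mix, by hand.** Take m = 2 sites each and ρ = 0.5 for both variables.

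- Within slope = rw.
- Slope across patient means = [ρ·rb + (1−ρ)·rw/m] / [ρ + (1−ρ)/m].
- Random-intercept slope = w·within + (1−w)·between, where w = W/(W+B), W = SSW/σe² and B = SSB/(σe² + mτ²). Here σe² and τ² are the residual site and patient variances at the fitted slope.
- SSW = 15 × 1 × 0.5 = 7.5. SSB = 14 × 2 × 0.75 = 21.

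*No local association (rb = 0.6, rw = 0).* Between slope = 0.30/0.75 = 0.40. At a fitted slope near 0.20, σe² = 0.5 × 1.04 = 0.52 and τ² = 0.5 × (1 − 0.24 + 0.04) = 0.40, so σe² + 2τ² = 1.32. W = 7.5/0.52 = 14.4; B = 21/1.32 = 15.9; w = 14.4/30.3 = 0.475. Pooled slope = 0.525 × 0.40 = 0.21. Simulation gives 0.195.

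*Purely local association (rb = 0, rw = 0.6).* Between slope = 0.15/0.75 = 0.20. At a fitted slope near 0.45, σe² = 0.5 × (1 − 0.54 + 0.2025) = 0.331 and τ² = 0.5 × 1.2025 = 0.601, so σe² + 2τ² = 1.534. W = 7.5/0.331 = 22.6; B = 21/1.534 = 13.7; w = 22.6/36.3 = 0.623. Pooled slope = 0.623 × 0.6 + 0.377 × 0.2 = 0.45. Simulations give 0.44 to 0.46, against about 0.60 for the within-patient slope.

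**Step 2: how often the pooled slope looks positive with no local association.** Simulated trials of 15 patients with a mean of about two sites, rb = 0.6, rw = 0, two-sided 0.05:

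| Assumed ICC | Random-intercept slope significant | Within-patient slope significant |
|---|---|---|
| imaging 0.15, marker 0.4 | about 8% | about 5% |
| both 0.3 | 11-12% | 4-6% |
| both 0.5 | 18-20% | 4-6% |
| both 0.7 | 31-34% | 4-6% |

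A further set of runs with a different mix of sites gave 8%, 17% and 27% for the last three rows. With no association at either level the random-intercept test rejects in 5-6% of trials, so clustering itself is handled.

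**Step 3: GEE.** The mixing is the same: at ICC 0.5 the exchangeable GEE slope averages 0.19, against 0.20 for the random intercept. Rejection rates from the uncorrected sandwich variance are not used to size the problem. With 15 clusters that test already rejects in about 12-17% of trials when there is no association at all, which is a different defect.

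**Step 4: precision of the separated slope.** The within-patient slope has about 30 − 15 − 1 = 14 degrees of freedom. With both correlations at 0.6 (ICC 0.5), power is about 0.72, against 0.95 for the pooled slope. With a purely local 0.6 the two are about equal (0.72 and 0.71).

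**The case against.** The strongest reply has four parts.

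- **The estimand is partly read in.** Matching tissue to image location is met by co-registration whichever slope is reported, and Section 3.5 criticises earlier work mainly because tissue did not come from the imaged region. Section 3.6 is interested in heterogeneity across tumours as well as within them, and looks ahead to FLT as a marker of prognosis. This stands in part: a between-patient association is a legitimate result here. It does not remove the within-tumour interest stated in Sections 1.1 and 3.5, and the two should be distinguishable.
- **The size rests on assumed ICCs.** Sites are chosen for contrasting uptake within each tumour (Sections 4.2 and 4.3), which spreads imaging values within patients and favours a low imaging ICC. This stands, and is why the range starts at about 8%.
- **The plan is exploratory and open.** Section 11.0 disclaims strict hypothesis tests, its model list is only illustrative, and scatter plots come first. This stands: a split is not excluded. But none is planned, and an ambiguous descriptive slope still misinforms the later studies it is meant to support.
- **Tumour type is partly covered** by the second analysis restricted to high-grade gliomas. This stands for metastasis and PCNSL, but not for newly diagnosed against recurrent disease.

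A reader might go further and infer that the study will present a between-patient correlation as a local one, or that its false-positive rate is badly inflated. The documents support neither. They never say that the slope will be labelled within-tumour, they handle clustering in the standard error, and the percentages above depend on assumed inputs.

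**Conclusion.** The concern holds as a gap in what the analysis can show, not as an error in how it handles correlated data. A single-slope random-effects or GEE model gives a mix of two associations, so by itself it cannot support a statement about local tracking of Ki67 or CD31, or a local comparison of SUV with k3.

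The size is conditional. The distortion is slight if imaging values vary mostly within tumours, and substantial if patients differ strongly on both measures. It also runs in both directions, since a purely local relation is understated. The mixing itself does not depend on any particular ICC; only its size does. Because the analyses are exploratory, the consequence is a wrong steer for later work rather than a false confirmatory claim.

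**What to change.** In each regression for the primary aim and Secondary Aim #2, replace the raw imaging variable by two terms: the patient's mean over accepted sites, and the site's deviation from that mean. Report three estimates with confidence intervals, all labelled exploratory: the deviation slope (within-tumour), the patient-mean slope (between-patient) and the pooled slope. State how many patients contribute two or more accepted sites. If GEE is used, name a small-sample variance correction.

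The cost is one extra model term and the added lines of output, with no new patients, scans or tissue. Patients with a single accepted sample add nothing to the within-tumour slope, and post-hoc rejection of biopsies may increase their number. That slope is also less precise when the two levels agree, which is the reason to keep the pooled slope beside it.

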### Schema:

- a. Evaluation and consent of 15 patients with initial presentation of presumptive glioblastoma based on MRI appearance.
- b. Baseline pretreatment MRI studies following injection of gadolinium (GdDTPA) and pre-surgical dynamic  $^{18}\text{F}$ -FLT PET study with CT for attenuation correction.
- c. Planned tumor resection volume will be pre-determined by the operating neurosurgeon using anatomic MRI per routine, who will be blinded to the results of the preoperative PET study.
- d. Two neuroradiologists and a nuclear medicine attending, blinded to the surgical planning, will independently select "patterns of interest" or sites of heterogeneity within the tumor on co-registered PET-MRI scans for targeted biopsy.
- e. Surgical resection will take place per routine with frameless stereotactic tracking of resection location, updated by intraoperative MRI (iMRI, 1.5T Siemens magnet).
- f. Histopathological and molecular characterization of the biopsied tumors: immunohistochemical staining for MIB-1 and gene expression profiling.
- g. Data analysis: physician interpretation of brain MRI and PET scans; volumetric region-of-interest (ROI) analysis for derivation of tumor and contralateral brain activity;  $^{18}\text{F}$ -FLT time activity curves (TACs) and steady-state SUVs; non-invasive determination of plasma TACs (venous and arterial input curves); voxel-based and ROI-based pharmacokinetic modeling.

Memorial Sloan-Kettering Cancer Center  
IRB Protocol

IRB#: 09-060 A(4)

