Post-hoc mapping of biopsy sites into presurgical image coordinates will determine which samples were in fact within the target ROI. The primary limitation of the approach is that it relies on the surgeon's estimation of where an ROI has shifted intraoperatively in order to direct biopsies: it is possible that some ROIs may be missed or deemed to be outside the resection volume and hence unavailable for biopsy. However, the minimum proposed ROI size of 1.0 cm^3 is within the range of intraoperative accuracy routinely used by neurosurgeons during resection to avoid vascular and neuroanatomic structures. Therefore it is anticipated that at least one specimen be taken from the vicinity of the ROI, as judged by the surgeon; it will be established post-hoc as being accurately mapped to within an ROI. Acquiring tissue from surgically exposed tumor, as proposed here, avoids the significant risk of parenchymal bleeding from deep needle biopsy. If difficulties are encountered implementing the above plan, needle biopsy sampling through an initial minimal surgical exposure will be employed under a separate IRB-approved protocol.

Biopsy specimens will be acquired for research purposes after pathologic specimens are submitted for the patient per routine by neurosurgery. A minimum of 1.0 g of biopsy tissue will be acquired per patient for research purposes, as the priority for the study is histologic validation. We will ensure that as much tissue as possible is sent for histology, aiming for roughly half of the specimens to be further processed as frozen sections for research purposes.

Biopsy specimens will be frozen immediately in liquid nitrogen and stored at -80 °C until later use. All biopsy cores will be divided in half, with one half of the frozen tissue specimen sectioned for RNA and DNA expression analysis, and the remaining half processed as a formalin-fixed paraffin-embedded (FFPE) specimen for immunohistochemistry by fixing the tissue in 10% neutral buffered formalin for 2 days, followed by paraffin embedding. Tissue markers for tumor cell proliferation (MIB-1) and

**IRB  
PB**

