**IRB#: 09-060 A(4)**

number of samples from each tumor that represent differential features. For larger sample sets, simple Venn intersection may reveal core signature genes. Sparser samplings of feature contrasts will be analyzed by pairwise Gene Set Enrichment to identify a subset of mutually expressed signature genes.

Analysis of gene signatures: Gene signatures representing contrasting imaging features will be compared with known signatures representing previously described molecular subclasses of GBM, including the "Proneural", "Proliferative" and "Mesenchymal" classes, as well as molecular subclasses already emergent in the analysis of 206 GBM samples in The Cancer Genome Atlas pilot project to date. Signatures will be compared by GSEA and gene ontology. GSEA will also be used to analyze feature-derived signatures in an exploratory process to characterize possible enrichment for altered expression within canonical pathways. The Connectivity Map offers another potentially valuable resource for mining feature-derived signatures, and can be approached with specific hypothesis: that differential proliferation and permeability, as image-derived features, may be associated with transcriptome evidence of PI3 kinase signaling or VEGF signaling, both of which are well represented in the database. Analysis will include exclusion of gene subsets such as cell cycle members whose differential regulation is likely to correlate with simple histologic measures of proliferation.

For the exploratory aim, we can evaluate the power we will have to detect a difference in gene expression levels between areas of high and low tracer uptake (or signal intensity) within an individual. With 15 subjects contributing a sample from both a high and low uptake area, we expect to be able to detect a twofold difference in base 2 log intensity levels with a Type I error of 0.001 and a Type II error of 0.05 if the standard deviation for the expression levels is 0.75 (using base 2 logarithms) or less. A standard deviation of 0.75 is within the range of what we expect to see.

Sample size justification:

For this pilot study, we expect there to be 15 eligible patients per year, and we will aim to reasonably accrue 8 of these patients per year for two years.

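### The expression-aim power statement needs 15 complete high/low pairs, which the plan does not secure and its own expected yield makes unlikely

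*Combined protocol and SAP*

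**What the plan says.** The target is 15 patients throughout. The Schema in Section 1.1 begins with "Evaluation and consent of 15 patients with initial presentation of presumptive glioblastoma", Section 4.2 enrols 15 and Section 4.3 scans 15. Section 11.0 (Statistical Methodology for Primary Aim) gives one reason to go further, a metastasis or PCNSL found at surgery: "If it does occur, however, we will continue accrual until 15 high grade glioma patients have been enrolled". No section says what happens when a patient with confirmed glioma yields no accepted specimen or no high/low pair.

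Section 4.2 (Primary Aim Study Design) acknowledges that tissue may be lost: "it is possible that some ROIs may be missed or deemed to be outside the resection volume and hence unavailable for biopsy". It also says that non-linear registration after surgery will decide which samples are accepted and which rejected, and that research tissue is taken only once routine pathology has enough.

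The planning figures are in Section 11.0. For the exploratory aim, the power statement rests on this condition: "With 15 subjects contributing a sample from both a high and low uptake area". It claims detection of a twofold difference with Type I error 0.001 and Type II error 0.05 at a standard deviation of 0.75 in base 2 logarithms. Under Sample size justification, a correlation figure is given for data on 15 patients with one observation each. The text then adds "we expect an average of two observations for each patient (up to four samples per patient"), and sets the accrual aim: "we will aim to reasonably accrue 8 of these patients per year for two years".

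**The concern.** The stopping rule counts enrolled glioma patients, whereas the expression-aim power counts patients with two usable specimens of opposite kind. Nothing in the plan connects the two counts. A patient whose targets are missed, lie outside the resection volume or are rejected on mapping still fills one of the 15 places. So does a patient who gives two high-uptake samples and no low one.

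At stake is a stated operating characteristic. A reader planning the larger study would take 95% power for a twofold change as what this pilot could do, and would weigh a thin or absent signature accordingly. If the pairs number 10 or 12, that reading is wrong. The same gap touches the Ki67 and CD31 relationships in the primary aim and Secondary Aim #2, where 15 is the most patients that can contribute tissue if accrual ends at 15, not the number to be relied on.

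**Working it through.** **Inputs from Section 11.0.** 15 pairs; Type I error 0.001; Type II error 0.05; SD 0.75 (log2); a twofold difference; an average of two observations per patient, up to four; accrual of 8 a year for two years, which is 16.

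**Readings the text leaves open, taken as assumptions.** Twofold is 1.0 on the log2 scale. The test is two-sided. The SD of 0.75 is that of the within-patient difference.

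**Step 1: reproduce the plan's figure.** Normal formula: n = ((z(0.9995) + z(0.95)) × SD / difference)² = ((3.291 + 1.645) × 0.75 / 1.0)² = 13.7, so 14 pairs. At 15 pairs, power = Φ(√15 / 0.75 − 3.291) = Φ(5.164 − 3.291) = 97%. The stated 95% is therefore met at 15 pairs under this formula and this reading of the SD.

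The SD reading matters. If 0.75 were instead the SD of a single sample and the two samples were uncorrelated, the SD of the difference would be 0.75 × √2 = 1.06. The same formula would then give 64% at 15 pairs.

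**Step 2: can the stated yield give 15 pairs?** An average of two over 15 patients is 30 observations. Fifteen pairs use 15 × 2 = 30, which leaves none over. So every patient must give exactly two, one high and one low. Any patient with three or four implies another with fewer than two, who cannot form a pair. A patient with two samples of the same kind also has no pair.

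**Step 3: power with fewer pairs.** The normal column is Φ(√n / 0.75 − 3.291). The t column is the probability that a noncentral t, with n − 1 degrees of freedom and noncentrality √n / 0.75, exceeds the two-sided 0.001 critical value.

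| Complete pairs | Normal formula | Paired t-test |
|---|---|---|
| 15 | 97% | 81% |
| 13 | 94% | 67% |
| 12 | 91% | 59% |
| 10 | 82% | 39% |
| 8 | 68% | 20% |

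By the normal formula 14 pairs still give 95.5%, and the stated 95% is lost at 13 or fewer. By the paired t-test it is not reached at 15, and 20 pairs are needed.

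**Step 4: which analyses need tissue?** The relationships of K1 to k4 with Ktrans compare imaging with imaging, and Secondary Aim #1 compares two k3 estimates from the same scan. Neither needs a specimen. The Ki67 and CD31 relationships, Secondary Aim #2 and the expression aim do.

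**The case against.** The strongest reply is that the power sentence is a conditional illustration in a study whose analyses are declared purely exploratory, with no rigorous hypothesis testing planned. The documents give no loss rate. Section 4.2 describes safeguards: several biopsies around each target, an expectation of at least one specimen near it, a minimum of 1.0 g of tissue per patient, and needle sampling under a separate protocol if difficulties arise. The average of two appears beside the correlation and concordance figures, not in the expression calculation. Section 11.0 also says the expression methods will depend on how many samples each tumor provides, and gives pairwise gene set enrichment as the approach for sparser contrasts.

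Much of this stands, and it limits the point. A reader might infer that 15 contributing patients will not be obtained. The documents do not support that; they support only that 15 are not assured. A reader might also infer that patients without tissue add nothing to any aim, which Step 4 contradicts. Nor can the likely number of pairs be read from the plan. For example, assume four targets per patient, two high and two low, each accepted independently with probability 0.5. That matches the average of two and gives (1 − 0.25)² × 15 = 8.4 pairs. But the model is an assumption: if about two targets are available and both are sampled, patients with no specimen would be rare.

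The reply does not rescue the stated figure. The safeguards concern tissue near a target, not one high and one low sample in each patient. The fallback for sparse contrasts changes the analysis and does not restore 95% power. The average of two is the plan's only stated expected yield, and the expression samples come from the same biopsies.

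**Conclusion.** The point holds for the expression-aim power statement. Its 15 complete pairs are not assured, and they are unlikely at the plan's own average of two with up to four. By the normal formula the claimed 95% fails at 13 or fewer pairs and falls to 68% at 8. By the paired t-test it is 81% at 15 and 20% at 8. These figures rest on the three readings listed in the working.

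The fall from 97% to 81% at a full 15 pairs comes from the choice of formula and should not be attributed to accrual. Only the decline down each column is due to missing pairs.

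For the Ki67 and CD31 relationships and Secondary Aim #2, 15 patients with data is an upper bound. Whether the correlation power stated for 15 patients is itself right is a separate question, not judged here. The PET-versus-MRI part of the primary aim and Secondary Aim #1 are untouched. Given the exploratory status, this is a stated figure to correct rather than a reason to redesign accrual.

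**What to change.** - In Section 11.0 (Statistical Methodology for Exploratory Aim), replace the single figure for 15 pairs with power, or the detectable difference, over a range of complete pairs, for example 8 to 15. Label the range as an assumption. Use the paired t-test, and state its sidedness and whether 0.75 is the SD of the within-patient difference.
- Under Sample size justification, say that data on 15 patients is an upper bound for the Ki67 and CD31 relationships and Secondary Aim #2, and that the imaging-only analyses do not depend on specimens.
- Commit to reporting how many patients had no accepted specimen and how many had no high/low pair, with reasons. For a study of focal-biopsy feasibility this is a result in its own right.

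Replacing patients who yield no accepted specimen, within the planned 8 × 2 = 16, is optional. It would not by itself secure 15 pairs, and it may not secure 15 contributors. With a no-yield probability q, the chance of at least 15 contributors from 16 is (1 − q)^16 + 16q(1 − q)^15. That is 74% at q = 0.0625 and 46% at q = 0.11, both assumed rates.

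The cost is a few sentences of protocol text and two counts in the report, with no added patient. The downside is that the stated expression-aim power becomes less favourable.
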